Prior studies in children with Levodopa/carbidopa, have proposed that the improvement in visual acuity is related to a change in the neural network of the striate cortex (amblyopia treatment)³⁻⁸. In this study we propose that the retina itself in albinism is deficient in dopamine, and vision improvement will occur as a result of improved retinal function in response to the deficient neurotransmitter dopamine. This study has a pretest-post-test design in order to determine if improvement in vision is in response to replacement of deficiency (dopamine). The OCT will be a critical determinant to confirm vision improvement as a result of improved retinal function, but are not primary outcome data. Additionally, patients with albinism have been shown to have impaired color vision and contrast sensitivity, it is unclear if these visual functions will be affected by treatment, therefore data will be analyzed to determine if there is a treatment effect other than on visual acuity alone.

Main outcome measures will be collected at pre-treatment, 1 month, 3 months, and 4 months. Change in visual acuity as measured in logMAR by Snellen or SVEP after 3 months of treatment is the primary outcome.

Additional outcome measures will be collected at pre-treatment and 3 months, and will include color vision (Farnsworth 15 or 100 hue), contrast sensitivity, optical coherence tomography (OCT), and color photography.

Because of the issues of possible permanent vision loss due to amblyopia as mentioned above, it is important that the effect be studied in children under age 7, in whom the irreversible effect of amblyopia has not occurred. Additionally however, children under 3 years of age are generally not able to subjectively participate in some of the testing proposed in this study, therefore the lower age limit will be included to provide patients who will be able to complete the testing. Finally, older patients with albinism may still appreciate an improvement in vision function from replacement therapy, despite the fact that there may be a ceiling on the improvement in vision because of the pre-existing amblyopia. Older children and adults will be included to allow for optimum assessment of vision recovery at all ages and for ability to satisfactorily recruit the number of patients necessary. Further studies will need to be designed to study the effects in younger children, and to isolate the vision effect (if found) based on the amblyopia factor.

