In use in children this medication is available in liquid form and will be

prepared and dispensed by the UW/AFCH for subjects who are unable to swallow pills or take solid medications.

Patients will undergo a 3-month treatment period followed by a 1-month follow-up period. Visit length and testing is typical for an initial evaluation/consultation in the pediatric ophthalmology clinic. All testing is performed in the pediatric ophthalmology clinics by staff experienced and trained in visual testing of the pediatric population. The PI has 15 years of clinical experience in pediatric ophthalmology alone and is fellowship trained in pediatric ophthalmology, it is well within the ability of most all patients to perform these test within one setting except where noted based on age. In some cases it is expected that tests other than the primary outcome data may not be obtainable in all patients. Patients will be removed from the study if they cannot complete the primary outcome (visual acuity) testing. Other vision testing (color testing, SVEP, Contrast, photography, and OCT) will be requested, but not required to participate in the study. Please see schedule of visits below for detail.

Research Design:

Patients with Oculocutaneous albinism will be recruited ages 3 and up, weight greater than 25 pounds. Entrance into the study is dependent upon clinical evidence of decreased or absent pigmentation in skin, hair, and eyes. No ocular only albinos will be recruited. Additionally, all patients enrolled in the study will be requested but not required to undergo genotyping (TYR and OCA2) gene) of their form of albinism, if not already known. These two types of albinism are the most common, and, for most clinical observers - indistinguishable. However, the presence or absence of TYR theoretically has a direct impact on expected visual response to dopamine replacement. The genotypic form of albinism has no known implications for other aspects of health, clinical care. overall health prognosis or insurability. Indeed, because the genotype has no influence on diagnosis or treatment, it is expected that less than one in ten patients recruited will have been previously tested. Testing will be performed by a certified national clinical lab with validated testing. No "out of pocket" expense for this test will be incurred by the family of the patient. Costs for testing will be covered by funding from the UW Department of Ophthalmology.

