tid (mg)		
60	25-33	11-15
75	34-47	>15-21
100	48-60	>21-27
125	61-74	>27-34
150	75-89	>34-40
200	90-117	>40-53
250	118-134	>53-61
300	135-159	>61-73
4mg/kg/day	>160	>73

Confidentiality:

A physician or clinical technician trained in ophthalmology or

ophthalmologic photography will perform data collection during the clinical visit in a private setting. All procedures will be consented to.

All records, including the data collection forms, will be coded numerically to keep the data separate from any patient identification. A log that includes the subject identification and assigned code will be stored independently from the data. Data will be stored in a locked office or on an isolated hard-drive desk top computer which is password protected and can only be accessed by the PI. The hard drive of the PI is backed-up hourly. In addition, the study coordinator will have access to the paper charts used to monitor the treatment and adverse events. No study data or subject logs will be stored on portable laptop computers. Photos will not be stored with study data, only reviewed from the medical record.

Study Schedule:

I -- Pretreatment

- 1 Informed Consent/Assent
- 2 Blood pressure, heart rate, weight.

Elevated blood pressure will need to be under control by the primary care provider prior to entry into the study.

- 3 Ophthalmic Exam complete with cyclopentolate 1% dilation (standard dilation drops used in the pediatric clinic in children over 20 pounds)
 - a. Snellen visual acuity or HOTV
- b. Color vision Farnsworth 15 or 100 hue, patients old enough to participate (estimated 6 years old and up)
- c. Sweep visual evoked potential (VEP) (standard test in clinical setting -10 min test patients "watch a computer monitor" while recordings are made of vision response)
 - d. Contrast Sensitivity (5 min test on contrast board)
 - e. Color photography (Only performed If not current within the last 3 yrs) (all photos and Optical Coherence Tomography (OCT) take about 10mins)

predilation iris and full face postdilation fundus postdilation OCT

- 4 Optional Blood draw for genetic subtype analysis if unknown (5ml purple tube).
 - 5 Females who are pregnant, lactating, or intending to become pregnant within the next 12 weeks. A negative urine pregnancy test will be required for all females who have had a menstrual cycle.
- II 1 day, 1 week and 1-month treatment phone call check compliance, and adverse events.

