- III -- 3 months treatment—prior to wash-out/weaning Drug count/compliance, adverse event monitoring.

- 1 Ophthalmic Exam complete with dilation
 - a. Snellen visual acuity or HOTV
 - b. Color vision Farnsworth 100 hue
 - c. Sweep VEP
 - d. Contrast Sensitivity
 - e. Color photography postdilation fundus postdilation OCT
- 2 Blood pressure, heart rate
- 3. Taper of medications over 6 days as outlined (3 days of twice daily dosing, then 3 days of once daily dosing).

IV – 4-month 1 month post treatment

- 1 Ophthalmic exam nondilation
 - a. Snellen acuity
 - b. Color vision 15 Hue
 - c. Sweep VEP
 - d. Contrast Sensitivity

Pharmacology:

Carbidopa/Levodopa oral commercially available

Storage: Store at 25°C (77°F), excursions permitted to 15-30°C (59-86°F).

Protect from light.

Dosage: 4mg/kg/day Levodopa orally, 1mg/kg/day Carbidopa, in three equally

divided doses.

Disallowed medications:

- Clorgyline
- Iproniazid
- Pargyline
- Phenelzine
- Procarbazine
- Selegiline
- Toloxatone
- Tranylcypromine
- Apomorphine
- Bitolterol
- Desipramine
- Dobutamine
- Dopamine
- Epinephrine
- Isocarboxazid
- Isoetharine

- Isoniazid
- Isoproterenol
- Linezolid
- Methyldopa
- Moclobemide
- Nialamide
- Norepinephrine
- Venlafaxine
- Bromperidol
- Bupropion
- Droperidol
- Ferric Ammonium Citrate
- Fosphenytoin
- Indinavir
- Iron
- Kava

- Metoclopramide
- Phenylalanine
- Phenytoin
- Spiramycin

- Phenothiazines
- Risperidine
- Tyrosine

Rescue medication/overdose: Management of acute over dosage with Carbidopa Levodopa is the same as management of acute over dosage with Levodopa. Pyridoxine is not effective.

General supportive measures should be employed, along with immediate gastric lavage. Intravenous fluids should be administered judiciously and an adequate airway maintained. Electrocardiographic monitoring should be instituted and the patient carefully observed for the development of arrhythmias; if required, appropriate antiarrhythmic therapy should be given.

Clinical lab: none

Data/Safety monitoring:

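### The visit schedule does not keep each patient on one colour-vision test, so patients started on the 15 hue have no same-test comparison of baseline with month 3

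*Combined protocol and SAP*

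**What the plan says.** Study Objectives describes the trial in these terms: "This study has a pretest-post-test design". It lists colour vision among the secondary measures: "Additional outcome measures will be collected at pre-treatment and 3 months, and will include color vision (Farnsworth 15 or 100 hue), contrast sensitivity". For functions such as colour vision and contrast sensitivity the stated aim is that "data will be analyzed to determine if there is a treatment effect other than on visual acuity alone". The same section says that colour testing "will be requested, but not required to participate in the study".

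The Study Schedule then gives a colour-vision item at three visits:

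- Pretreatment, item 3b: "Color vision Farnsworth 15 or 100 hue, patients old enough to participate (estimated 6 years old and up".
- 3 months, item 1b: "Color vision Farnsworth 100 hue".
- 4-month visit, item 1b: "Color vision 15 Hue".

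The documents do not say how the pre-treatment test is chosen, do not require the same test to be repeated, and give no common score or conversion between the two tests.

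**The concern.** The trial has one arm, so a colour-vision effect can be seen only as a within-patient change. That change is interpretable when both measurements come from the same test. If the test changes between baseline and month 3, the difference combines a change of instrument with any effect of the drug, and there is no control group from which to estimate the instrument part.

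The schedule as written produces this situation for some patients. Because no rule governs the choice at pre-treatment, the patients left with a usable pair could also be a selected group. The documents neither show nor exclude that.

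**Working it through.** There is no colour-vision sample size or power figure in the plan to reproduce. The check is to set the three schedule entries side by side and see which pairs of visits share a test.

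Inputs, all from the Study Schedule: pre-treatment is the 15 or the 100 hue; month 3 is the 100 hue; month 4 is the 15 hue. Two sequences are therefore possible.

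| Test at pre-treatment | Sequence | Baseline to month 3 | Month 3 to month 4 | Baseline to month 4 |
|---|---|---|---|---|
| 15 hue | 15, 100, 15 | different tests | different tests | same test |
| 100 hue | 100, 100, 15 | same test | different tests | different tests |

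**Baseline to month 3** (the declared comparison). Let q be the share of colour-tested patients who start on the 15 hue. The share with a same-test pair is 1 − q. The plan does not give q, so as illustrations only:

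- q = 0: 1 − 0 = 100% keep the pair.
- q = 20%: 1 − 0.20 = 80%.
- q = 50%: 1 − 0.50 = 50%.
- q = 80%: 1 − 0.80 = 20%.
- q = 100%: 1 − 1 = 0%.

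These shares should not be turned into patient counts by multiplying by 30. The 30 in the Statistical section is the whole trial, whereas colour testing is optional and is expected only from about age 6 in a trial that enrols from age 3. The number tested is not stated.

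**Month 3 to month 4.** The share with a same-test pair is 0 for every q, because the schedule names a different test at each of these visits.

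**Baseline to month 4.** The share with a same-test pair is q. This pair spans treatment and withdrawal together, so it shows net change after washout. It shows neither the change on drug nor the change on stopping.

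**Comparison with Study Objectives.** That section gives either test for both pre-treatment and month 3, while schedule item III-1b gives only the 100 hue at month 3. The two do not agree. Study Objectives does not list month 4 for colour vision, although the schedule measures it then.

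**The case against.** The strongest reply is that Study Objectives allows the 15 hue at month 3, so a team working from that section could keep a patient on one test throughout. The schedule is also abbreviated elsewhere: the 4-month visit lists Snellen acuity without the HOTV alternative, and the 3-month colour item drops the age qualifier. On this view the 3-month entry is shorthand and not a deliberate restriction. This stands in part. It means that the plan contradicts itself, and it cannot be said that the plan firmly requires a switch of test. It does not remove the problem, because the visit list is what clinic staff would follow, and Study Objectives does not itself require the same test at both visits. Staff could give both tests, but nothing tells them to.

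A second reply is that little depends on this outcome. Colour vision is additional and optional, with no stated effect size or power. That is correct and limits the weight of the point.

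A reader might infer that the colour-vision data are unusable for everyone. The documents do not support that. Patients started on the 100 hue keep the declared comparison, and those started on the 15 hue keep baseline to month 4. Only the month 3 to month 4 comparison is missing for all, and no analysis of it is declared.

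A reader might also infer that the 15 hue goes to younger or less able patients because it is shorter, so that the analysable group is selected on age or vision. The documents give no duration for either colour test and no rule for choosing between them, so this remains a possibility and not a finding.

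**Conclusion.** The point holds as an inconsistency with a real consequence for a declared additional outcome. If the Study Schedule is followed literally, every patient started on the 15 hue lacks a same-test baseline-to-month-3 pair. The size of that loss cannot be computed: it runs from none to all of the colour-tested patients, depending on a share that the plan does not state. The absence of any same-test month 3 to month 4 pair is certain under the schedule but is the lesser part.

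The conclusion assumes that one test is given per visit, that the schedule governs over Study Objectives where they differ, and that no conversion between the tests is available, since none is given. The primary logMAR analysis and both sample size calculations are untouched. The change is worth making because it is cheap, not because the trial's main conclusion depends on it.

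**What to change.** - Keep schedule item I-3b with its age qualifier, and add: *record which test was used*.
- Change items III-1b and IV-1b to: *the same Farnsworth test (15 or 100 hue) used for that patient at pre-treatment*.
- Align Study Objectives with this wording, and state there whether month 4 is a colour-vision time point.
- State in the Statistical section that change in colour vision is analysed within test type only, never across tests, and that the number of patients with a same-test pair is reported for each test. This rule can also be applied to data already collected.

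The cost is a few lines of text. Both tests are already in the plan, so no new test is introduced. The one practical consequence is that patients started on the 100 hue would take the 100 hue at month 4, where the schedule now gives the 15 hue.

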Recently, work in several areas of dopamine deficient states (Parkinson disease, cocaine withdrawal disorder, Phenylketomuria) has shown that retinal tissue is one of the richest in the concentration of dopamine. Indeed, 15 different visual functions and 13 types of dopamine retinal pathologies have been attributed in some way to the retinal dopamine system³. The extent to which the absence of dopamine in the retina of patients with albinism affects their visual function is unknown.

Levodopa/carbidopa replacement therapy has been used and studied in children with amblyopia since 1992⁴. This therapy has been shown to be safe and effective in the treatment of children with amblyopia at dosages of up to 3mg/kg/day body weight⁷. Standard treatment in children with Dopa responsive dystonia (DRD) is 10mg/kg/day.¹⁷ Levodopa/carbidopa has also been studied as a treatment in children with retinal disease⁵ and shown to have a beneficial effect, however none of the patients in this report carried the diagnosis of albinism.

The use of Levodopa/Carbidopa has been approved by the FDA for

treatment of Parkinson's disease. As such, it was not specifically tested in patients less than 18 years of age. Subsequently, it has been shown to be a safe and effective treatment in multiple studies as an off-label use for the treatment of amblyopia in children under 10 years old without adverse effect³⁻⁸. It also has been used by pediatric neurology for treatment of children with dystonia. Parkinson's disease typically requires increasing doses of Levodopa/carbidopa over many years, and eventually side effects occur. In contrast, children with Dopa-responsive dystonia often have complete resolution of symptoms on very low doses of Levodopa/carbidopa, with no need to increase the dose over time. Exceptions to this have been reported.¹⁶

Study Objectives:

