Information collected from the record will include patient's age, sex, race, genotype of albinism (if known) and the outcome measures listed above, results of clinical testing will be recorded in the clinic chart in addition to a study chart and research will only be recorded in the study chart. Research tests including results of genotyping will not be shared with subjects or family. For females who have had a menstrual cycle, positive results of screening pregnancy tests will be given to the subject in private, not shared with the parent.

Patients include OCA1a patients, OCA1b, OCA2, and unclassified OCA. OCA1a patients clinically are known to have the worst vision, and physiologically have the lowest (or absent) levels of tyrosinase function (Dopamine Production). All patients will be treated with Levodopa/carbidopa 4mg/kg/day in three divided doses (Dose determination outlined below). Patients and their families will be asked to submit the costs of medication to their insurance companies or cover the costs themselves, if this cost is not covered by their insurance. Per the UW Pharmacy, the pricing for 30 Carbidopa/Levodopa tablets is \$27.81, the oral suspension would cost \$32.32 for 100 mL. Subjects under 135 pounds would require an oral suspension provided by the UW pharmacy, in order to control the appropriate dose. This formulation has been adapted from The Hospital for Sick Children (University of Toronto). The ingredients for this formulation consist of: Carbidopa 25 mg/Levodopa 100 mg tablets (quantity = 5), Ora-Plus 50 mL, and Ora-Sweet 50 mL. Subjects over 135 pounds could obtain the drug at an outside pharmacy. Treatment will continue for 3 months followed by a six day taper reduction in dose (3 days at twice per day and 3 days at once per day), as a rapid reduction in dosage can be associated with fever, stiff muscles, confusion, abnormal thinking, fast or irregular heartbeat, and sweating. Side effects reported in adults with Parkinson's disease on Levodopa/carbidopa will be monitored (see schedule) and include nausea, headache, mood changes, insomnia, nightmares, dizziness, tiredness, leg pain, tinnitus and emesis. (These have not been reported in studies of Levodopa/Carbidopa in children)

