Adverse events will be monitored by the study coordinator, who will record the events on AE collection forms, and report events upon discovery to the PI and co-investigators. Adverse events will be monitored at each visit, and during the phone interview on days 1, 7, and 30 after first dose of medication (see attached AE form) and patients/parents will be given the AE form and phone number of the study coordinator to report these events. The PI and co-investigators will review each adverse event and confirm if it is related, serious, or expected. Adverse event reports will be reviewed for possible trends, the PI and/or co-investigator would consider modifying or stopping the study in the event of an emerging pattern of events. The study team will report such events to the IRB in accordance with the posted guidance. If a patient is withdrawn from the study (either by themselves, a guardian, or the study staff) prematurely or the study is stopped, they will be contacted by phone to assure that the medication is tapered correctly (3 days at twice per day and 3 days at once per day) and asked to return for a post-treatment visit.

Risks:

Risks of entering this study arise from three potential areas. These potential areas are:

- Medication risks
- Clinical testing risks, and
- Confidentiality risks

As stated above, while this medication has not been tested by the FDA in children, however its use in children dates as early as 1993. In general, the side effect profile in patients without Parkinson's disease (the primary FDA indication) is considerably less. Adverse events recording will include the 16 possible side effects reported in the literature. Subjects will be withdrawn from the study and

instructed on tapering of medication if the AE is of significant severity that the subject, their guardian, or the PI feel continuation is not justified. Please see AE reporting form.

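### No adverse-event or compliance contact is scheduled between the day-30 call and the 3-month visit (about 60 of 90 dosing days); one call at about day 60 would be a cheap improvement

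*Combined protocol and SAP*

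**What the plan says.** Three parts of the protocol set the contacts during dosing, and they agree.

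- **Data/Safety monitoring** has AEs monitored at each visit and "during the phone interview on days 1, 7, and 30 after first dose of medication". Between contacts, "patients/parents will be given the AE form and phone number of the study coordinator to report these events". The same section provides for subjects who withdraw or are withdrawn: staff telephone them to see that the drug is tapered correctly and ask them back for a post-treatment visit.
- **Study Schedule, item II** puts the calls at 1 day, 1 week and 1 month and gives their content: "treatment phone call check compliance, and adverse events".
- **Study Schedule, item III** is the 3-month visit, before the taper: "Drug count/compliance, adverse event monitoring".

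Study Objectives adds that "Main outcome measures will be collected at pre-treatment, 1 month, 3 months, and 4 months", whereas the Study Schedule lists only a call at 1 month.

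On the population, Research Design says "Patients with Oculocutaneous albinism will be recruited ages 3 and up", and Background says of the drug that "it was not specifically tested in patients less than 18 years of age". The discontinuation paragraph, next to the first sample-size statement, wants an early stop and its reason recorded and the patient still asked to attend for data collection.

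**The concern.** All the scheduled telephone contact falls in the first third of treatment. In the last two thirds nobody on the study team is due to ask how the subject is or whether the drug is still being taken. Little else is scheduled that would show a problem: blood pressure and heart rate are taken only at pretreatment and 3 months, and the protocol lists no clinical laboratory tests.

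Two things are at stake, both modest. The first is active AE enquiry. Several of the monitored effects (mood change, insomnia, nightmares, tiredness) are ones a family may not think to report in a young child, and Data/Safety monitoring relies on AE reports being reviewed for trends. The second is knowledge of a stop that nobody reports. The family's reporting route is described for AEs. If a family quietly stops the drug, the next planned check is the drug count at month 3, when the date and reason would rest on recall.

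**Working it through.** The plan gives contact days but no gap length, so there is no stated figure to reproduce. The check is the difference between consecutive scheduled contacts.

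**Inputs**
- First dose: day 0.
- Calls: days 1, 7 and 30 (Data/Safety monitoring; Study Schedule, item II).
- Next contact: the 3-month visit (Study Schedule, item III). Taking this as day 90 is an assumption; days 84 and 92 show the range.
- Taper: six days after the 3-month visit, so outside the period counted.

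**Formula:** gap = contact day minus previous contact day; share = longest gap / dosing days.

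| 3 months taken as | Gaps as written | Longest (share) | Gaps with a day-60 call | Longest (share) |
|---|---|---|---|---|
| day 84 | 1, 6, 23, 54 | 54 (54/84 = 64%) | 1, 6, 23, 30, 24 | 30 (30/84 = 36%) |
| day 90 | 1, 6, 23, 60 | 60 (60/90 = 67%) | 1, 6, 23, 30, 30 | 30 (30/90 = 33%) |
| day 92 | 1, 6, 23, 62 | 62 (62/92 = 67%) | 1, 6, 23, 30, 32 | 32 (32/92 = 35%) |

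Scheduled contacts during dosing rise from 4 to 5.

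**Does the 1-month outcome point in Study Objectives shorten the gap?** No. Whether month 1 is a call or a visit, it falls at about day 30, and the interval to month 3 is the same.

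**How many subjects could still get the call?** The Statistical section reports 19 completed subjects and an updated size of 30.
- If 30 is the total and only those 19 have been dosed: 30 − 19 = 11 at most.
- The same section still carries a recruitment limit of 50, which would give 50 − 19 = 31 at most.
- The number is smaller if others are already past day 60, or if the look at 22 completers ends the trial (22 − 19 = 3 more completers needed).

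**Coordinator time**, with call length assumed at 10 minutes (range 5 to 20):
- 11 subjects: 11 × 10 = 110 min = 1.8 h (55 min = 0.9 h to 220 min = 3.7 h).
- 31 subjects: 31 × 10 = 310 min = 5.2 h (155 min = 2.6 h to 620 min = 10.3 h).

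**What cannot be computed.** The documents give no rate of unreported AEs or unreported stops, so neither the number found nor the time saved in learning of them can be derived.

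**The case against.** The strongest reply is that this is a preference. The sections agree with each other and no rule in the protocol is broken. Calls weighted to the first month suit a drug with no planned dose increase. Families can report AEs at any time, and the withdrawal provisions cover stops that the team is told about. The instruction to document a stop sets no deadline, so the month-3 check can still meet it. The AE form and the consent pages are not in the text and may tell families to report a stop.

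The protocol's account of safety in children is also reassuring:
- Background cites multiple amblyopia studies in children under 10 without adverse effect.
- Risks dates paediatric use to 1993.
- The dose rationale puts the study dose at less than half the usual dose for dopa-responsive dystonia in children (4 against 10 mg/kg/day).
- Of the listed side effects the protocol says "These have not been reported in studies of Levodopa/Carbidopa in children".

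Most of this stands. It fixes the rating at optional and removes any claim of a known late risk. One qualification is that Background's safety statement for amblyopia covers doses up to 3 mg/kg/day, and this trial gives 4. What the reply does not remove is that every route open in the last two months of dosing depends on the family making the contact.

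A reader might infer more than the documents support:
- **That subjects are unmonitored for two months.** They are not; the gap is in scheduled contact, and a reporting route stays open throughout.
- **That the schedule is an error or contradicts itself.** On AE and compliance contacts the sections match.
- **That the call would halve the delay in learning of a stop.** This needs an assumed timing and frequency of unreported stops, and the documents supply neither.
- **That the primary result is compromised.** The paired logMAR comparison with baseline is the same analysis with or without the call.

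**Conclusion.** The point holds as a low-priority design improvement. As written, the longest interval without a scheduled AE or compliance contact is about 60 of 90 dosing days (54 to 62 days, 64% to 67%, for 3 months taken as 84 to 92 days). A call at about day 60 brings it to about 30 days (30 to 32). These figures rest only on the stated contact days and the assumed length of 3 months.

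The benefit is confined to asking about AEs rather than waiting for them, and to possibly learning sooner of a stop nobody reported. Its size is unknown. It reaches few subjects: at most about 11 on the target of 30, assuming only the 19 completers have been dosed. The case for acting is that the change costs very little in a trial that enrols from age 3.

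**What to change.** Add one coordinator call at about day 60 to item II of the Study Schedule and to the list of call days in Data/Safety monitoring, for every subject not yet at day 60 when the amendment takes effect. Use the existing AE and compliance check, and ask directly whether the drug is still being taken. Record at which contact each AE was first reported. Clinical action on what is found stays under the existing rules.

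Costs and downsides:
- A minor amendment and a few coordinator hours, with no new visit, procedure or staff.
- Fuller AE ascertainment in later subjects than in earlier ones, within one small single-arm dataset. The AE report should say which subjects had no day-60 call, whether because they had already passed day 60 or because they had withdrawn.
- A possible small effect on adherence in the last month of dosing in those later subjects. The documents do not allow this to be sized; it should be noted when results are described. The primary analysis method itself stays as it is.

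If hardly any subjects are still before day 60, leaving the schedule alone is reasonable.

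### No symptom check is scheduled before first dose in this single-arm trial, so the relatedness and trend reviews lack a prespecified pre-dose reference; using the existing adverse event form once at baseline is a cheap improvement

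*Combined protocol and SAP*

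**What the plan says.** All references are to the combined protocol and SAP.

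- **Design.** Research Design puts every patient on the study drug. It justifies the absence of a comparison group by the stability of vision in albinism and does not discuss background symptoms.
- **What is collected.** The Risks section states: "Adverse events recording will include the 16 possible side effects reported in the literature". Research Design names ten effects to be monitored: "nausea, headache, mood changes, insomnia, nightmares, dizziness, tiredness, leg pain, tinnitus and emesis". It adds that these have not been reported in paediatric studies of the drug. The adverse event form is cited as an attachment and is not in the supplied text.
- **When, according to Data/Safety monitoring.** "Adverse events will be monitored at each visit, and during the phone interview on days 1, 7, and 30 after first dose of medication".
- **When, according to the Study Schedule.** Part I (pretreatment) lists consent, "Blood pressure, heart rate, weight", eye tests, an optional blood draw and a pregnancy test. Part II is the "treatment phone call check compliance, and adverse events" at 1 day, 1 week and 1 month. Part III (3 months, before the taper) includes "Drug count/compliance, adverse event monitoring". Part IV (4 months) begins with "Ophthalmic exam nondilation" and lists only eye tests.
- **How events are used.** "The PI and co-investigators will review each adverse event and confirm if it is related, serious, or expected". The same section has reports reviewed for trends, and the investigators would consider modifying or stopping the study if a pattern appeared. It gives no relatedness criteria, comparison rate or baseline comparison.

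**The concern.** Several of the named effects are everyday complaints: headache, tiredness, insomnia, mood changes, nightmares, leg pain. With no untreated group, the natural reference for such a complaint is the same patient before the first dose. Study Objectives describes a before-and-after design, and vision is handled that way. Symptoms are not: the schedule has no pre-dose measurement of them.

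Errors could go in either direction. A complaint the patient already had may be judged drug-related or add to an apparent trend. A real new symptom may be dismissed as long-standing. Enrolment starts at age 3, so onset may have to be recalled by a parent after dosing has begun. A pre-dose record cannot be reliably recovered later.

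**Working it through.** The plan states no adverse event rate, threshold or safety power, so there is no figure of its own to reproduce. The check sets the two accounts of adverse event collection side by side.

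| Contact | Drug status | Adverse event item in Study Schedule | Covered by Data/Safety monitoring |
|---|---|---|---|
| I, pretreatment | before dosing | none | only if the visit wording is read to include it |
| II, calls at 1 day, 1 week, 1 month | on drug | yes | yes, by day |
| III, 3 months | on drug, before taper | yes | yes, as a visit |
| IV, 4 months | after taper | none | yes, as a visit |

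The schedule names adverse events at 3 calls + 1 visit = 4 contacts, all on drug.

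**Possible references for relatedness and trend review**

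1. *Control arm:* none.
2. *Paediatric rate:* none. Research Design says the named effects have not been reported in children and gives no figure.
3. *Pre-dose record:* none scheduled. The items that Research Design takes from the record are age, sex, race, genotype and the outcome measures, not symptom history.
4. *Off-drug visit at 4 months:* available in principle under the monitoring sentence. It follows exposure, and its schedule lists no adverse event item.
5. *Rule linking an event to a baseline:* none in the text.

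**How many patients a change could reach**

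The Statistical section reports 19 completed subjects and a revised size of 30. It also gives an enrolment limit of 50.

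- At 30: 30 − 19 = 11 patients at most.
- At 50: 50 − 19 = 31 patients at most.

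Both are upper limits, because further patients may already have been dosed without having completed.

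**The case against.** The strongest reply is that a baseline entry cannot be ruled out. The monitoring sentence refers to visits without exception, and the unsupplied form may record prior status or onset date. This stands: a reader might infer that the form is first used after dosing starts, but the documents do not establish that. What remains is that the schedule lists adverse events at parts II and III and not at I or IV, and that no comparison with baseline is stated.

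A reader might also infer that background complaints will be counted as drug effects. The documents do not support this. The investigators judge each event individually and can ask whether it predates dosing, and no analysis of adverse event counts is described. Misattribution is a risk, not a certainty. Retrospective questioning by investigators who know the patient is on drug is still weaker than a record made beforehand.

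Nor is it right that there is no reference at all, or that the trend review is the only safety trigger. The 4-month visit gives a weak within-patient comparison. The exclusions for depression, neurologic disease and peptic ulcer remove some sources of background symptoms. The Risks section separately allows withdrawal on the severity of an event, which does not depend on counts.

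Finally, it is tempting to put a number on the problem. Assume 30 patients, 4 on-drug contacts and 16 items: 30 × 4 × 16 = 1,920 answers. Assumed background rates of 2%, 3% or 5% give 38.4, 57.6 or 96 positives with no drug effect. These figures should not be used:

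- The rates are not in the documents, which also do not say that every item is asked at every contact.
- If answers are independent at rate p, a baseline form removes only a fraction p of later positives: 38.4 × 0.98 = 37.6, 57.6 × 0.97 = 55.9, 96 × 0.95 = 91.2. That is a reduction of 2% to 5%. The form helps with persistent symptoms, which this model leaves out.
- The count uses all 30 patients, although 19 had already completed.

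**Conclusion.** The point holds as a cheap improvement. No symptom check is scheduled before first dose, the scheduled adverse event items all fall on drug, and no pre-dose reference is prespecified for the relatedness and trend decisions. Pre-existing complaints may therefore be misattributed to the drug, or new ones dismissed.

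The size cannot be computed from the documents, and none is claimed. The conclusion rests on the schedule being the operative list of visit procedures. If the form is already completed at pretreatment under the visit wording, the remaining gaps are that the schedule does not show it and that no treatment-emergent definition uses it. The primary visual acuity analysis is unaffected either way.

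**What to change.** 1. In Study Schedule part I, list completion of the existing adverse event form before first dose, with a stated recall period (for example, the past week).
2. In part IV, list the same form explicitly, so that schedule and monitoring section agree.
3. In Data/Safety monitoring, define a treatment-emergent event as a symptom that is new or worse than on the patient's baseline form.
4. Use that definition to inform the relatedness judgement and the trend review, while still recording and reviewing all events.

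The cost is a few minutes per patient at visits already held, plus one definition. No extra patients are needed. Patients dosed without a baseline form, which on the schedule as written includes the 19 completed subjects, cannot acquire one and should be reported separately. The benefit is therefore limited to at most 11 of a planned 30, or more only if enrolment continues towards 50.
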